3.2 SECONDARY ENDPOINTS

1. SPR one month after the first injection and at every month until Month 6 inclusive and at months 9 and 12.
2. Percentage of subjects with anti-HBs antibodies titer $\geq 100\text{mIU/ml}$ at Month 0, and then at every month until Month 7 inclusive and at months 9 and 12.

	Protocol No.: SciB018
	Version and Date: Version 2.0, September 9, 2015 Amendment 1

- The geometric mean concentration (GMC) as determined by anti-HBsAg antibody titers at Month 0, then at every month until Month 7 inclusive and at months 9 and 12.

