4.4 Primary Endpoint Analysis

The primary endpoint of the study is the Seroprotection rate (SPR), defined as the proportion of subjects with anti-HBs antibody titer at least equal to 10mIU/ml, at Month 7 (i.e. one month after the third immunization with Sci-B-Vac™). In the first Interim Analysis the primary endpoint will be tested on month 4. Subjects early terminated from the study for any reason at any time while having an anti-HBs antibody concentrations ≥ 10 mIU/ml will be considered among those who met endpoint.

The principal analysis of the primary endpoint will employ a non-inferiority analysis [SAS PROC FREQ with binomial (noninf margin=0.09 p=(1- α) exact)] statement will be used for testing the below hypothesis:

H0: $P-p_0 \leq -\text{Margin}$

H1: $P-p_0 > -\text{Margin}$

Where p_0 , the assumed true SPR is 95% and the non-inferiority margin is 9.0%, employing that study will be considered successful if the lower bound of the (1- α) exact CI will be 86.0% or more.

The rate of responders will be calculated along with 95% confidence interval using Exact binomial method. The final population for statistical analysis will include only subjects who fully comply with the study protocol, have no inclusion/exclusion criteria violation and subjects who early terminated the study but reached the primary endpoint prior to withdrawal (mITT population).

Comparative analysis will be applied for baseline characteristics (such as gender, smoking status, age and BMI) between non seroprotected subjects (i.e. anti-HBsAg antibody<10), seroprotected subjects (ie. anti-HBsAg antibody ≥ 10 mIU/ml) and subjects with Anti-HBs ≥ 100 mIU/ml.

Age categories will be defined by intervals of 5 or 10. BMI will be defined <25 or ≥ 25 . Smoking status will be defined using 5 categories:

Never

Past-smoker;

Light smoker (up to 10 cigs/day)

Moderate smoker (10-19 cigs/day)

Heavy smoker (20 or more cigs/day) BMI categories will be defined <25 and ≥ 25

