4.5 Secondary Endpoints Analysis

The secondary endpoints for the study are:

- SPR one month after the first injection and at every month until Month 6 inclusive and at months 9 and 12.
- Percentage of subjects with anti-HBs antibodies titer ≥ 100
- mIU/ml one month after the first injection and then at every month until Month 7 inclusive and at months 9 and 12.
- The geometric mean concentration (GMC) as determined by anti-HBsAg antibody titers at Month 0, then at every month until Month 7 inclusive and at months 9 and 12.

SPR at all time-points as defined above will be analyzed using the principal analysis method as defined for the primary endpoint, and will be presented graphically as well.

The percentage of subjects with anti-HBs antibodies titer ≥ 100 mIU/ml will be calculated from the responders sub-set at each available time-point. Subjects with titer >10 mIU/ml and <100 mIU/ml will be defined 'low-responders'.

The geometric mean concentration (GMC) as determined by anti-HBsAg antibody titers one month after the first injection and at every month until Month 7 inclusive and at months 9 and 12 will be calculated with 95% confidence intervals. Graphical presentation of GMC by month will be generated.

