5. APPENDIX I: TABLES TO BE INCLUDED IN THE STATISTICAL REPORT

Table number	Table Title
14.1	Demographic and Baseline Data
14.1-1.1	Disposition of subjects
14.1-1.2	Primary reason for early discontinuation
14.1-2.1	Analysis population
14.1-3.1	Demographic and Baseline data, ITT
14.1-4	Medical History, ITT
14.1-5	Baseline Physical Examination, ITT
14.1-6	Any Concomitant Medication, ITT
14.1-7	Any Concomitant Non-drug Medication, ITT
14.1.2	Exposure to Sci-B-Vac injection
14.1.2.1	Sci-B-Vac injection, ITT
14.2	Efficacy Analysis
14.2-1	Seroprotection rate (SPR) by Month, mITT
14.2-2	Seroprotection rate (SPR) by Month, FT (for first IA mITT who completed month 7 will be presented)
14.2-3	Secondary Endpoint Analysis: Percentage of Subjects with Anti-HBs \geq 100 mIU/ml by Month, mITT
14.2-4	Secondary Endpoint Analysis: Percentage of Subjects with Anti-HBs \geq 100 mIU/ml) by Month, FT (for first IA mITT who completed month 7 will be presented)
14.2-5	Geometric means of anti-HBs antibody titers by month, mITT
14.2-6	Geometric means of anti-HBs antibody titers by month, FT (for first IA mITT who completed month 7 will be presented)
14.2-7	Frequency of gender by responders (SPR) (at month 4 for first IA)
14.2-8	Frequency of age categories by responders (SPR) (at month 4 for first IA)
14.2-9	Frequency of Responders (SPR) by Smoking status and month (month 4 for IA)
14.2-10	Frequency of Responders (SPR) by BMI categories and month (at month 4 for first IA)
14.2-11	Geometric means of anti-HBs antibody titers by month and Gender
14.2-12	Geometric means of anti-HBs antibody titers by month and age categories
14.2-13	Geometric means of anti-HBs antibody titers by month and Smoking status
14.2-14	Geometric means of anti-HBsAg antibody titers by month and BMI categories
14.2-15	Serologic Markers for Hepatitis B Infection, ITT
14.3	Safety Data
14.3.1	Adverse Events
14.3.1	Summary Incidence of TEAE (Treatment Emergent Adverse Events), ITT
14.3.1-1	Summary of Adverse Events by SOC and PT, ITT

Table number	Table Title
14.3.1-2	Summary of Adverse Events by SOC and PT and Severity, ITT
14.3.1-3	Summary of Adverse Events by SOC and PT and Relation to study drug, ITT
14.3.1-4	Summary of Serious Adverse Events by SOC and PT, ITT
14.3.2	Listing of SAEs (if applicable)
14.3.2-1	Listing of Serious Adverse Events
14.3.4	Abnormal Laboratory Results
14.3.4-1	Incidence of Hematology Abnormal Clinically Significant Results
14.3.4-2	Out of Range Hematology Results

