7. APPENDIX III: FIGURES

Figure number	Title
Figure 1	SPR by month, mITT
Figure 2	SPR by month, FT (for first IA mITT who completed Month 7)
Figure 2.1	Percentage of non-responder, responder and high-responder to Sci-B-Vac™ by Month, mITT (second interim analysis)
Figure 3	Geometric Mean of anti-HBs Antibody titers by month, mITT
Figure 4	Geometric Mean of anti-HBs Antibody titers by month, FT (for first IA mITT who completed Month 7)
Figure 5	Geometric Mean of anti-HBs Antibody titers by month and Gender
Figure 6	Geometric Mean of anti-HBs Antibody titers by month and Age
Figure 7	Geometric Mean of anti-HBs Antibody titers by month and Smoking status
Figure 8	Geometric Mean of anti-HBs Antibody titers by month and BMI

* Box plots for laboratory results and vital signs will be generated for specific parameters, based on the results and the sponsor's request.

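### SAP 4.5 computes the ≥100 mIU/ml percentage among responders only, while the endpoint definition and table titles say percentage of subjects

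*SAP*

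**What the plan says.** **The definition.** Protocol v2.0, 3.2 Secondary Endpoints, gives the endpoint as "Percentage of subjects with anti-HBs antibodies titer" ≥100 mIU/ml. The same wording returns in Protocol v2.0 10.7.2, SAP 2.5 and the endpoint list that opens SAP 4.5. None of these restricts it to responders. Protocol v2.0 10.7 assigns secondary efficacy endpoints to the mITT set.

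**The outputs.** In SAP Appendix I, Table 14.2-3 is titled "Secondary Endpoint Analysis: Percentage of Subjects with Anti-HBs" ≥100 mIU/ml by month, on mITT. Table 14.2-4 has the same title on the other set ("100 mIU/ml) by Month, FT").

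**The analysis rule.** Below its endpoint list, SAP 4.5 says the percentage "will be calculated from the responders sub-set at each available time-point". The next sentence defines low-responders as subjects above 10 and below 100 mIU/ml.

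**Responder.** The term is not formally defined. SAP 4.4 refers to the primary result as the rate of responders, and Table 14.2-9 is titled "Frequency of Responders (SPR) by Smoking status and month". Both point to subjects at ≥10 mIU/ml at the visit in question.

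**The concern.** Two tables whose titles promise a percentage of subjects would, under the SAP 4.5 rule, show a share of responders. Non-responders would drop out of a measure of how many vaccinees reach a high titre.

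One secondary objective is to characterise the immune response throughout the study, and this endpoint is reported visit by visit. If the denominator is each visit's responders, it changes as SPR changes, so the visits are no longer comparable. The figure is also undefined at any visit without responders.

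The SAP's mITT set (2.4) already leaves out subjects who did not receive all three injections and did not reach seroprotection. A responder denominator would be a second filter on non-response, and the table titles do not disclose it.

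**Working it through.** **Inputs**
- Threshold for SPR: ≥10 mIU/ml (SAP 2.5). Threshold for this endpoint: ≥100 mIU/ml.
- Expected Month 7 SPR: 95% (SAP 2.6).
- Success rule (SAP 4.4): the lower limit of the "exact CI will be 86.0% or more". The 86% is a lower confidence limit, not an observed SPR.
- N = 70 (SAP 2.6, sample size justification), 84 (Protocol v2.0, 5.1) and 92 (SAP 2.4).
- First interim: Month 4, about 95% seroprotected among at least 50 subjects (SAP 2.7 and 4.4).
- The documents give no SPR for earlier visits and no expected share at ≥100 mIU/ml, so there is no stated figure for this endpoint to reproduce.

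**Per-visit reading (responders = subjects at ≥10 mIU/ml at that visit)**

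Everyone at ≥100 is also at ≥10, so

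share of responders at ≥100 = (share of subjects at ≥100) / SPR

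excess = (share of responders at ≥100) × (1 − SPR) ≤ 1 − SPR

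**Month 7**

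The lowest SPR at which the trial still succeeds is the smallest count whose exact (Clopper-Pearson) lower limit reaches 86%.

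| Case | Exact lower limit | One fewer | SPR | Factor 1/SPR | Maximum excess (points) |
|---|---|---|---|---|---|
| Expected SPR | – | – | 95% | 1/0.95 = 1.053 | 5.0 |
| 66/70, two-sided 95% | 86.01% | 65: 84.11% | 94.3% | 1.061 | 5.7 |
| 79/84, two-sided 95% | 86.65% | 78: 85.10% | 94.0% | 1.063 | 6.0 |
| 86/92, two-sided 95% | 86.34% | 85: 84.95% | 93.5% | 1.070 | 6.5 |
| 85/92, one-sided 95% | 86.18% | 84: 84.86% | 92.4% | 1.082 | 7.6 |

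The first interim, at about 95% SPR, gives about 1.05.

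**Earlier visits (assumed SPRs)**

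The factor is 1/0.50 = 2 at SPR 50% and 1/0.20 = 5 at SPR 20%. In counts, with N = 70 and about 80% of responders assumed to be at ≥100:

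| SPR | Share of responders | Share of subjects |
|---|---|---|
| 20% | 11/14 = 78.6% | 11/70 = 15.7% |
| 50% | 28/35 = 80.0% | 28/70 = 40.0% |
| 80% | 45/56 = 80.4% | 45/70 = 64.3% |
| about 95% | 53/66 = 80.3% | 53/70 = 75.7% |

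The gaps are about 63, 40, 16 and 5 points. If about 50% of responders reach ≥100 instead, they are about 40, 26, 10 and 3 points.

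**Trend**

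Let p1 and p2 be the shares of subjects at ≥100 at two successive visits. A rise among subjects is reported as a fall when 1 < p2/p1 < SPR2/SPR1. Assume SPR goes from 50% to 95% and the share of subjects at ≥100 goes from 40% to 70%. The reported figures are 40/50 = 80.0% and then 70/95 = 73.7%.

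**Fixed-set reading (responders = Month 7 responders, complete data)**

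The share at ≥100 at any visit is at most (share of subjects at ≥100) / (Month 7 SPR). The factor is therefore at most 1.05 to 1.08 at the SPRs above. The denominator is constant, so it cannot reverse a trend.

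**The case against.** **Numerator reading.** The sentence might only say where the ≥100 group is drawn from, with mITT or FT still the denominator as the table titles state. This does not hold up. Everyone at ≥100 mIU/ml is already at ≥10, so restricting the numerator to responders changes nothing. The phrase has an effect only as a denominator.

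**Figure 2.1.** SAP Appendix III plans a figure headed "Percentage of non-responder, responder and high-responder to" Sci-B-Vac by month on mITT. Its natural denominator is the whole set, and by the second interim all subjects will have had their three injections, so it should cover the early visits. That is a real mitigation, but the figure is tied to that one analysis and does not correct Tables 14.2-3 and 14.2-4.

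**The large effects are assumed.** This stands. The documents support a factor of about 1.05 to 1.08 at Month 7 and about 1.05 at the Month 4 interim. The factors of 2 and 5 and the trend reversal only illustrate what low early SPRs would do.

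**Readers can convert back.** Multiplying by the SPR in Table 14.2-1 ("Seroprotection rate (SPR) by Month, mITT") or 14.2-2 recovers the defined endpoint, but only for a reader who knows that the title and the denominator disagree. The conversion may also be slightly approximate. Early terminators at ≥10 mIU/ml count as meeting the primary endpoint, and no matching rule is given for ≥100.

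**No decision hangs on it.** This stands too. SAP 4.5 applies the non-inferiority method to SPR, and no success rule is attached to the ≥100 percentage.

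**Conclusion.** The contradiction is real. The endpoint definition and the table titles say subjects; the analysis rule says responders; no text reconciles them, and the SAP version-history entries for 4.5 do not mention a change of denominator. Followed as written, the rule gives a mislabelled figure.

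On the per-visit reading, which the SAP's own use of the term supports best, the figure is too high whenever SPR is below 100%. The size is modest at Month 7 (factor 1.05 to 1.08, at most 5.0 to 7.6 points). At early visits it is unknown but possibly large. On a fixed Month 7 responder reading the factor stays at or below 1.05 to 1.08 at every visit, but the mismatch with the definition remains.

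The primary endpoint, SPR, GMC and the success rule are not touched. This should be corrected, but it does not threaten the trial's main conclusion.

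**What to change.** In SAP 4.5, replace the responder sub-set with all subjects of the table's analysis set, using the same visit denominator as the SPR tables (14.2-1 and 14.2-2), and state that denominator explicitly. This means mITT for Table 14.2-3 and FT for Table 14.2-4. At the first interim, Table 14.2-4 uses the mITT subjects who completed Month 7, as its title already says. State also how early terminators are classified for ≥100 mIU/ml.

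If the share of responders at ≥100 mIU/ml is wanted, show it as a separately labelled supplementary column with responder defined there.

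In the same edit, align the low-responder class to ≥10 and <100 mIU/ml. SAP 4.5 now starts it above 10, so a seroprotected subject at exactly 10 mIU/ml falls in neither the low-responder nor the ≥100 class.

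The core change costs one phrase in SAP 4.5 and the denominator in two table programs. The early-terminator rule, the boundary correction and the optional column with its definition add a few lines. No new data are needed.

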4.6 Exploratory Endpoints Analysis

The exploratory endpoints for the study are:

- The anti-preS1 antibody titers measured at Month 0, then at every month until Month 7 inclusive and at months 9 and 12.
- The anti-preS2 antibody titers measured at Month 0, then at every month until Month 7 inclusive and at months 9 and 12.

The geometric mean concentration (GMC) at Month 0, then at every month until Month 7 inclusive and at months 9 and 12 will be displayed across time in order to establish the kinetic of the immunological response during the study.

4.7 Safety analysis

4.7.1 Adverse Events

Adverse events will be recorded from the time when a subject has signed the Informed Consent Form and throughout the study, including the follow-up period. The MedDRA dictionary will be used to standardize the terms used by the investigator to describe the Adverse Events. The following were incorporated into the analyses which will include only Treatment Emergent Adverse Events (TEAEs), namely, events that have started on the day of first study dose or afterwards.

- Summary incidence of adverse events.
- The incidence (no. of subjects) and frequency (no. of events) of TEAEs broken down by System Organ Class (SOC) and by Preferred Term (PT) according to MedDRA dictionary.
- The incidence (no. of subjects) and frequency (no. of events) of TEAEs by SOC, PT and by Severity of event.
- The incidence (no. of subjects) and frequency (no. of events) of TEAEs by SOC, PT and by Relation to study drug.
- The derived dictionary used in the analyses (listing of full glossary).
- Listing of SAEs (regardless if started before or after first study dose) of randomized and dosed subjects captured in the clinical database until database drop date.
- Listing of Non-Treatment Emergent AEs.

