6.1.2 Visit 2 - First Vaccine Administration: Month-0 (Day 1)

Dosing day will be designated "**Month 0, Day 1**".

The subjects will be admitted to the CRC in the morning of treatment. They will be interviewed by the CRC study personnel regarding change in concomitant medications or changes to their health status since the Screening visit. Female subjects will undergo a urine pregnancy test, and eligibility of inclusion/exclusion criteria will be reviewed.

Prior to dosing (within 60 min before vaccination), the following activities will be completed:

- Vital signs, measured following 3 min rest (sitting BP, HR, RR and oral temperature);
- A blood sample for serology, safety laboratory testing and for further investigational purposes (55 ml) will be drawn.
- Urine sample will be collected for safety testing.

Vaccine administration: Each subject will receive the injection as described in Section 7.3. The time, date of vaccination and side of injection (i.e. left or right arm) will be documented in the CRFs and on the CRC Drug Administration Records.

After vaccination: Subjects remain in the CRC for approximately 1 hour after injection. Vital signs (sitting BP, HR, respiratory rate, and oral body temperature) will be measured at 60 (\pm 15) minutes after treatment, and recorded as appropriate.

Before discharge from the CRC a study physician will examine the injection site using a grading score (Appendix C).

The subjects will then be released from the CRC following a study physician's approval.

6.1.3 Visit 3 - Second Vaccine Administration: Month 1, (Week 4 \pm 3 days)

	Protocol No.: SciB018
	Version and Date: Version 2.0, September 9, 2015 Amendment 1

The second vaccination will take place 28 (± 3) days after the first vaccination (Visit 2). The previous injection site will be inspected before the second administration. Procedures will be identical to Visit 2, except the volume of blood drawn for serology, safety laboratory testing and for further investigational purposes, which will be lower (40 ml).

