6.4.1 Adverse Events (AEs)

AEs will be recorded continuously starting from the signing of the ICF through the Study Termination visit, in those subjects who have been actually dosed.

AEs reported prior to dosing will be recorded in the CRF and considered non-treatment emergent AEs. Any new systemic effect that occurs between scheduled visits should be brought to the attention of the Investigator and recorded in the subject's medical file and in the CRF.

The systemic symptoms will be graded according to the FDA Guidance to Industry²⁹ (see grading scale in Appendix C Table 3).

	Protocol No.: SciB018
	Version and Date: Version 2.0, September 9, 2015 Amendment 1

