6.4.3 Vital Signs

Vital signs (sitting systolic and diastolic blood pressure, heart rate, respiratory rate and oral temperature) will be measured after at least 3 minutes rest as per standard practice at the investigational site at the following time points:

- On screening,
- On each treatment visits (Visits 2, 3 and 8): within 60 minutes before vaccination, 60 (\pm 15) minutes after vaccination.
- On Study Termination visit

Changes in vital signs determined by the Investigator to be clinically significant will be noted as an AE on the appropriate CRF and in the subject's file. Such abnormalities will be closely monitored until stabilized or resolved.

Vital Signs will be graded according to the FDA Guidance to Industry²⁹ (see grading scale in Appendix C Table 2).

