6.4.6 Safety Laboratory Tests

Safety laboratory tests including biochemistry, hematology and urinalysis (see details in Appendix B) will be performed at the following times:

- On screening;
- On each treatment visits (Visits 2, 3 and 8): within 60 minutes before vaccination
- On Study Termination visit (without the screening serology tests)

All safety (chemistry, hematology urinalysis, serology and urine tests will be carried out by AML Laboratories, except urine test for pregnancy which will be performed at the trial site by the CRC staff.

	Protocol No.: SciB018
	Version and Date: Version 2.0, September 9, 2015 Amendment 1

Clinically significant laboratory tests or tests of unknown significance which are outside the normal range may be repeated as clinically indicated until the values return to normal, or until the etiology has been determined and the condition considered stable. Abnormal laboratory test results that are considered to be clinically significant by the investigator will be reported as an AE in the CRF.

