10.9 SAFETY ASSESSMENTS

10.9.1 Treatment Emergent Adverse Events

Adverse events will be recorded from the time when a subject has signed the Informed Consent Form and throughout the study, including the follow-up period. The MedDRA dictionary will be used to standardize the terms used by the investigator to describe the Adverse Events. The following were incorporated into the analyses which will include only Treatment Emergent Adverse Events (TEAEs), namely, events that were started on the day of first study dose or afterwards.

- The incidence (no. of patients) and frequency (no. of events) of TEAEs broken down by SOC and by SOC and Preferred Term according to MedDRA dictionary.
- The incidence (no. of patients) and frequency (no. of events) of TEAEs broken down by events attributes.
- The derived dictionary used in the analyses.
- Listing of SAEs (regardless if started before or after first study dose) of randomized and dosed subjects captured in the clinical database until database drop date.
- Listing of Non-Treatment Emergent AEs.

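### An adverse event that starts and is reported on Day 1 before the first injection is non-treatment-emergent under Protocol 6.4.1 but treatment-emergent under Protocol 10.9.1 and SAP 4.7.1

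*SAP*

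**What the plan says.** The references are to Protocol version 2.0 (Amendment 1) and the SAP.

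- **Protocol 6.4.1** splits at dosing: "AEs reported prior to dosing will be recorded in the CRF and considered non-treatment emergent AEs".
- **Protocol 10.9.1** splits by calendar day. TEAEs are "events that were started on the day of first study dose or afterwards".
- **SAP 4.7.1** repeats the calendar-day rule almost word for word: "events that have started on the day of first study dose or afterwards". It restricts the adverse event analyses to TEAEs and adds a separate listing of events that are not treatment-emergent.
- **Protocol 6.1.2 (Visit 2, Day 1)** places several procedures ahead of the first injection on the same day: "Prior to dosing (within 60 min before vaccination), the following activities will be completed". These are vital signs, a urine sample and blood: "A blood sample for serology, safety laboratory testing and for further investigational purposes (55 ml) will be drawn". After dosing, "Subjects remain in the CRC for approximately 1 hour after injection", with vital signs repeated.
- **Protocol 6.4.3 and 6.4.6** say when such measurements become adverse events. For vital signs: "Changes in vital signs determined by the Investigator to be clinically significant will be noted as an AE". For laboratory tests: "Abnormal laboratory test results that are considered to be clinically significant by the investigator will be reported as an AE in the CRF".
- **Protocol synopsis, Safety Assessments,** sets the primary safety endpoint in terms of adverse events after the vaccine has been given.

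**The concern.** The three sections do not define one boundary. Section 6.4.1 uses the moment of dosing, while 10.9.1 and the SAP use the date of dosing. The two boundaries differ during the part of Day 1 before the injection, when every subject has vital signs taken and gives blood and urine.

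An adverse event in that interval cannot have been caused by the vaccine and lies outside the stated safety endpoint. The date rule nevertheless puts it in the TEAE incidence, system organ class and preferred term, and severity tables. The trial has a single arm, so no comparator carries the same error and offsets it. If the wording stays as it is, whoever programs the tables will choose which rule applies.

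**Working it through.** The plan states no figure for this point, so the check sets the rules side by side and then works out the weight of one subject.

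**Step 1. Apply each rule to the possible Day 1 events.**

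| Event on Day 1 | Protocol 6.4.1 | Protocol 10.9.1 and SAP 4.7.1 |
|---|---|---|
| Starts and is reported before the injection (faintness at the draw; clinically significant pre-dose vital-sign change) | Not treatment-emergent | TEAE |
| Abnormality in a pre-dose sample, with the result and the significance judgement arriving after the injection | Unclear: the sample precedes dosing, the report follows it | TEAE if onset is dated Day 1 |
| Starts after the injection (local reaction within the observation hour) | Outside the pre-dose rule | TEAE |

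Only the first row is a direct contradiction. The second is an ambiguity, because 6.4.1 turns on when an event is reported and not on when it starts. The third row shows that Day 1 cannot simply be excluded: genuine reactions occur that day.

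**Step 2. Can the first row occur?** Yes. Protocol 6.1.2 puts these procedures within 60 minutes before the injection for every subject. The Day 1 draw is also the largest in the study. The volumes in Protocol 6.1.1 to 6.1.11 are 26, 55, 40, 35 × 4, 35, 50, 50 and 28 ml, which add up to the stated total of 424 ml.

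**Step 3. Weight of one subject.** SAP 4.7.1 reports both the number of subjects and the number of events.

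- Event count: each misclassified event adds 1.
- Overall TEAE incidence: a subject with such an event adds 1/N only if it is that subject's sole TEAE in the whole study. With N = 92 (SAP 2.4), 1/92 = 1.1 percentage points. With N = 84 (Protocol 5.1), 1/84 = 1.2 points.

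**Step 4. Scale, by assumption only.** The documents give no rate for such events. If between 1% and 5% of 92 subjects had one, that would be 0.01 × 92 = 0.9 to 0.05 × 92 = 4.6 subjects, or about 1 to 5. Overall incidence would rise by at most 1 to 5 points if none of them had any other TEAE, and by 0 if all of them did. Follow-up covers three injections and 12 months, so another TEAE is quite possible and the upper end is a bound, not an estimate.

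**Step 5. Can the data resolve it?** The time of vaccination is recorded in the CRF (Protocol 6.1.2). A time of onset is stated only for the SAE form (Protocol 9.4). For non-serious events the documents do not provide for placing a Day 1 event before or after the injection.

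**The case against.** The strongest case against is that this is a minor wording mismatch and that the date rule errs in the cautious direction. Few events are at stake. Vital-sign and laboratory findings become adverse events only when judged clinically significant. Subjects are screened healthy volunteers whose eligibility is reviewed again on Day 1, and events are recorded only in those actually dosed. This stands, and it limits the size of the point. It does not remove the contradiction.

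A reader might also infer stronger claims that the documents do not support:

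- *The SAP departs from the protocol.* It does not. Protocol 10.9.1 has the same date rule, so the inconsistency is already inside the protocol and the SAP carries one side of it forward.
- *All pre-injection findings on Day 1 are counted as TEAEs.* Only those recorded as adverse events with a Day 1 onset are. Pre-vaccination vital signs otherwise serve as baseline (SAP Appendix I, Table 14.3.13).
- *Pre-dose laboratory abnormalities are plainly non-emergent under 6.4.1.* Safety tests go to an outside laboratory, no turnaround time is given, and the rule depends on reporting.
- *Baseline findings are attributed to the vaccine.* TEAE status is a matter of timing. The investigator judges relationship separately, and an implausible time sequence is one criterion for the unrelated category (Protocol 9.1, Table 1). The event would still enter the overall, preferred-term and severity tables.
- *The same event is output twice.* Within the SAP, the events that are not TEAEs are the complement of the date-based set. Overlap arises only if 6.4.1 is applied to the listing and the date rule to the tables.

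**Conclusion.** The contradiction is real but narrow. For an adverse event that starts and is reported on Day 1 before the first injection, Protocol 6.4.1 gives one classification, and Protocol 10.9.1 and SAP 4.7.1 give the opposite. Under the SAP rule that event is counted in tables meant to describe what happened after vaccination. For pre-dose samples with later results, the plan is unclear rather than contradictory.

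The consequence is modest: one extra event per occurrence, and 1.1 percentage points of overall incidence per subject for whom it is the only TEAE, taking N = 92. How many subjects that would be cannot be derived from the documents. The seroprotection analysis is untouched. The point is worth settling before database lock because the correction is simple and the classification should not be left to programming.

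**What to change.** Use one definition in Protocol 6.4.1, Protocol 10.9.1 and SAP 4.7.1:

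1. A TEAE is an adverse event with onset at or after the time of the first injection, or one that worsens after it.
2. A laboratory or vital-sign adverse event is dated by the time of the sample or measurement, not by when the result was read or reported.
3. A Day 1 event whose order relative to the injection is unknown counts as a TEAE.

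This keeps true same-day reactions in the tables and retains the cautious default where information is missing.

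The cost is a short wording change in the three sections plus one data item. Injection time is already collected, but onset time is stated only for the SAE form. The adverse event page of the CRF therefore needs either an onset time or a before/after-injection flag for Day 1 events. For Day 1 events already entered, the flag would have to be completed from source documents, with rule 3 applied where they do not settle the order.
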